Clinical Trial Protocol: Study ST100-001

A Phase 2 Multi-Center, Randomized, Double Masked, Placebo Controlled Study to Assess the Safety and Efficacy of ST-100 Ophthalmic Solution in Subjects Diagnosed with Dry Eye Disease

Protocol Title: ST100-001
Protocol Number: ST100-001
Study Phase: 2
Investigational Product Name: ST-100 Ophthalmic Solution
IND Number: 143015
Indication: Dry Eye Disease
Investigators: Multi-Center
Sponsor: Stuart Therapeutics, Inc.
[name]
[name]
Contract Research Organization: Ora, Inc.
[name]
[name]
IRB/IEC:

Original Protocol: March 15, 2021
Protocol Amendment 1: May 21, 2021

Confidentiality Statement

This protocol contains confidential, proprietary information of Ora, Inc. Further dissemination, distribution or copying of this protocol or its contents is strictly prohibited.

SPONSOR PERSONNEL

Chief Medical Officer:	Tel: [REDACTED] Email: [REDACTED]
Senior VP, Research & Development:	Tel: [REDACTED] Email: [REDACTED]
Chief Scientific Officer:	Tel: [REDACTED] Fax: [REDACTED] Email: [REDACTED]

ORA PERSONNEL

Department Sr. Vice President:	Tel: [REDACTED] Fax: [REDACTED]
Department Associate Director:	Tel: [REDACTED] Fax: [REDACTED]
Clinical Project Manager:	Tel: [REDACTED] Fax: [REDACTED]

MEDICAL MONITOR

Medical Monitor:	Tel: [REDACTED] Cell: [REDACTED] Fax: [REDACTED]
-------------------------	--

SYNOPSIS

Protocol Title:	A Phase 2 Multi-Center, Randomized, Double Masked, Placebo Controlled Study to Assess the Safety and Efficacy of ST-100 Ophthalmic Solution in Subjects Diagnosed with Dry Eye Disease
Protocol Number:	ST100-001
Investigational Product:	
 1. Low dose ST-100 Ophthalmic Solution 2. High dose ST-100 Ophthalmic Solution 3. Placebo Ophthalmic Solution
Study Phase:	2
Objective(s):	The objective of this study is to compare the safety and efficacy of two different concentrations of ST-100 Ophthalmic Solution to placebo for the treatment of the signs and symptoms of dry eye.
Overall Study Design:	
Structure:	Multi-center, double-masked, randomized, placebo-controlled
Duration:	An individual subject's participation is estimated to be approximately 5 weeks (35 days)
Controls:	Placebo (vehicle minus active) Ophthalmic Solution
Dosage/Dose Regimen/ Instillation/Application/Use:	
Subjects eligible to be randomized will receive one of the following treatments to be administered bilaterally twice daily (BID) for 28 days (from Visit 2 to Visit 7).
 
[REDACTED]
 
During a 7-day study run-in period (for the purpose of subject selection) prior to randomization, all subjects will receive Placebo Ophthalmic Solution (Vehicle) bilaterally BID.

Summary of Visit Schedule:	
6 visits over the course of approximately 5 weeks
 
 • Visit 1 = Day -7 ± 1, Controlled Adverse Environment (CAE[®]) Screening • Visit 2 = Day 1, CAE[®] Confirmation / Baseline • Visit 3 = Day 2 ± 2 hours, 24 h recovery post-CAE[®] • Visit 4 = Day 4 ± 2 hours, 72 h recovery post-CAE[®] • Visit 5 = Day 8 ± 1 day, 1-Week CAE[®] Follow-Up • Visit 6 = Day 15 ± 1 day, 2-Week CAE[®] Follow-Up • Visit 7 = Day 29 ± 1 day, 4-Week CAE[®] Follow-Up and Study Exit
Measures Taken to Reduce Bias:	This is a randomized treatment assignment, double masked study
Study Population Characteristics:	
Number of Subjects:	Approximately 300 subjects will be screened to enroll 150 (50 per treatment arm) subjects

Condition/Disease:	Dry Eye Disease
Inclusion Criteria:	
Subjects must:	
1. Be at least 18 years of age; 2. Provide written informed consent; 3. Have a reported history of dry eye for at least 6 months prior to Visit 1; 4. Have a history of use or desire to use eye drops for dry eye symptoms within 6 months of Visit 1, except as noted in Exclusion Criterion (6) below; 5. Report a score of [REDACTED] on the Ora Calibra® Ocular Discomfort & 4-symptom questionnaire in at least one symptom pre-CAE® at Visits 1 and 2; 6. Have a Schirmer's Test score of [REDACTED] and [REDACTED] at Visits 1 and 2; 7. Have a conjunctival redness score [REDACTED] according to the Ora Calibra® Conjunctival Redness for Dry Eye Scale in at least one eye at pre-CAE® Visits 1 and 2; 8. Have a corneal fluorescein staining score of [REDACTED] in at least one region (e.g. inferior, superior, or central) pre-CAE® at Visits 1 and 2; 9. Have a sum corneal fluorescein staining score of [REDACTED] based on the sum of the inferior, superior, and central regions pre-CAE®, at Visits 1 and 2; 10. Have a total lissamine green conjunctival score of [REDACTED] based on the sum of the temporal and nasal regions pre-CAE® at Visits 1 and 2; 11. Demonstrate a response to the Controlled Adverse Environment (CAE®) at Visits 1 and 2 as defined by: a. Having at least a [REDACTED] point increase in fluorescein staining in the inferior region in at least one eye following CAE® exposure b. Reporting an Ora Calibra® Ocular Discomfort Score [REDACTED] at 2 or more consecutive time points in at least one eye during CAE® exposure [REDACTED]; 12. Have at least one single eye satisfy all criteria for 6, 7, 8, 9, 10 and 11 above.	
Exclusion Criteria:	
Subjects must not:	
1. Have any clinically significant slit lamp findings at Visit 1 that may include active blepharitis, meibomian gland dysfunction, lid margin inflammation, or active ocular allergies that require therapeutic treatment, and/or in the opinion of the investigator may interfere with study parameters; 2. Be diagnosed with an ongoing ocular infection (bacterial, viral, or fungal), or active ocular inflammation at Visit 1; 3. Have worn contact lenses within 7 days of Visit 1 or anticipate using contact lenses during the study; 4. Have used any eye drops within 2 hours of Visit 1; 5. Have previously had laser-assisted in situ keratomileusis (LASIK) surgery within the last 12 months; 6. Have used Restasis, Xiidra, or Cequa ophthalmic solutions within 45 days of Visit 1; 7. Have any planned ocular and/or lid surgeries over the study period or any ocular surgery within the last 6 months; 8. Have used, are using or anticipate using permanent or temporary punctal plugs during the study within 30 days of Visit 1; 9. Be currently taking any topical ophthalmic prescription (including medications for glaucoma) or over-the-counter solutions, artificial tears, gels or scrubs, or using a moisture chamber and cannot discontinue these medications for the duration of the trial (excluding medications allowed for the conduct of the study); 10. Be currently taking or have taken Omega-3 supplements within the last 3 months; 11. Have corrected visual acuity greater than or equal to logarithm of the Minimum Angle of Resolution (logMAR) [REDACTED] as assessed by Early Treatment of Diabetic Retinopathy Study scale in both eyes at Visit 1; 12. Be a woman who is pregnant, nursing, or planning a pregnancy;	

13. Be unwilling to submit a urine pregnancy test at Visit 1 and Visit 5 (or early termination visit) if of childbearing potential. Non-childbearing potential is defined as a woman who is permanently sterilized (e.g., has had a hysterectomy or tubal ligation), or is post-menopausal (without menses for 12 consecutive months);
14. Be a woman of childbearing potential who is not using an acceptable means of birth control; acceptable methods of contraception include: hormonal – oral, implantable, injectable, or transdermal contraceptives; mechanical – spermicide in conjunction with a barrier such as a diaphragm or condom; intrauterine device; or surgical sterilization of partner. For non-sexually active females, abstinence may be regarded as an adequate method of birth control; however, if the subject becomes sexually active during the study, she must agree to use adequate birth control as defined above for the remainder of the study;
15. Have a known allergy and/or sensitivity to the test article or its components;
16. Have a condition or be in a situation that the investigator feels may put the subject at significant risk, may confound the study results, or may interfere significantly with the subject's participation in the study;
17. Be currently enrolled in an investigational drug or device study or have used an investigational drug or device within 30 days of Visit 1;
18. Be currently using any medication known to cause ocular drying that is not used on a stable dosing regimen for at least 30 days prior to Visit 1;
19. Have a known history of meibomian gland procedures (e.g., LipiFlow, LPI, probing, etc.) within 6 months of study enrollment;
20. Be unable or unwilling to follow instructions, including participation in all study assessments and visits.

Evaluation Criteria:

Efficacy Measures and Endpoints:	
Primary Efficacy Measures: The following primary endpoints will be tested: The primary efficacy endpoint (sign) is:
• Total corneal fluorescein staining score on the Ora Calibra® scale, measured by [REDACTED] The primary efficacy endpoint (symptom) is:
• Ocular discomfort score on the Ora Calibra® Ocular Discomfort Scale, measured by [REDACTED] Secondary Efficacy Measures:
• Fluorescein staining (Ora Calibra® scale) at Visits 3, 4, 5, 6, and 7 (pre-CAE®, post-CAE®, and pre- to post-CAE®): regions: [REDACTED]• Lissamine green staining (Ora Calibra® scale) at Visits 3, 4, 5, 6, and 7 (pre-CAE®, post-CAE®, and pre- to post-CAE®): regions: [REDACTED]• Tear film break-up time at Visits 3, 4, 5, 6, and 7 (pre-CAE®, post-CAE®, and pre- to post-CAE®)• Conjunctival Redness at Visits 3, 4, 5, 6, and 7 (pre-CAE®, post-CAE®, and pre- to post-CAE®)• Drop comfort assessment after randomization at Visit 2• Ocular Surface Disease Index (OSDI) at Visits 3, 4, 5, 6, and 7 (pre-CAE®)• Four symptom questionnaire at Visits 3, 4, 5, 6, and 7 (pre-CAE®, post-CAE®, and pre- to post-CAE®)• Ocular discomfort during CAE® at Visits 4, 5, 6, and 7• Daily diary

---	---

	
• Visual Analog Scale – Burning/Stinging, Itching, Foreign Body Sensation, Blurred Vision, Eye Dryness, Photophobia, Pain at Visits 3, 4, 5, 6, and 7 (pre-CAE®)• Unanesthetized Schirmer's Test at Visit 7 (pre-CAE®)• Ocular Discomfort Scale outside of the CAE® at Visits 3, 4, 5, 6, and 7 (pre-CAE®, post-CAE®, and pre- to post-CAE®)
Safety Measures:	
• Visual acuity• Slit-lamp evaluation• Adverse event query• Intraocular pressure• Undilated fundoscopy
General Statistical Methods and Types of Analyses	
Analysis Populations	

• Intent-to-Treat Population – The intent-to-treat (ITT) population includes [REDACTED]• [REDACTED]• Per Protocol Population – The per protocol (PP) population includes [REDACTED]• [REDACTED]• Safety Population – The safety population includes [REDACTED]• [REDACTED]	
Sample Size	

This study is expected to enroll [REDACTED] subjects in each population, for a total of [REDACTED] randomized subjects. Approximately [REDACTED] subjects will be screened. Assuming a 10% drop out rate, [REDACTED] subjects per group are expected to complete the study.
	
Multiplicity Considerations	

Hierarchical fixed sequence testing will be used to maintain the type I error rate of [REDACTED]. The primary analysis will first evaluate the difference in the change in the total corneal fluorescein staining score from baseline (Visit 2, pre-CAE®) to Visit 7 (Day 29, pre-CAE®) between high-dose ST-100 and placebo. If the results are statistically significant in favor of high-dose ST-100 over placebo [REDACTED], then the study will be considered a success and high-dose ST-100 will be declared to be superior to placebo. Following the hierarchical fixed sequence testing, the following endpoints will be formally tested:
 
1. If the results of total corneal fluorescein staining score from baseline to Visit 7 (Day 29, pre-CAE®) between high-dose ST-100 and placebo are statistically significant in favor of high-dose ST-100 over placebo [REDACTED], then the difference in the change from baseline (Visit 2, pre-CAE®) of the ocular discomfort score on the Ora Calibra® Ocular Discomfort Scale to Visit 7 (Day 29, pre-CAE®) will then be evaluated in the high-dose ST-100 vs placebo groups.2. If the results of ocular discomfort score are statistically significant in favor of high-dose ST-100 over placebo [REDACTED], then the difference in the change in the total corneal fluorescein staining score from baseline (Visit 2, pre-CAE®) to Visit 7 (Day 29, pre-CAE®) between low-dose ST-100 and placebo will then be evaluated.3. If the results of the total corneal fluorescein staining score change from baseline (Visit 2, pre-CAE®) to Visit 7 (Day 29, pre-CAE®) are statistically significant in favor of low-dose ST-100 over placebo [REDACTED], then the difference in the change from baseline (Visit 2, pre-CAE®) in the ocular discomfort score on the Ora Calibra® Ocular Discomfort Scale to Visit 7 (Day 29, pre-CAE®) between low-dose ST-100 and placebo will then be evaluated.	

Should any primary endpoint in the hierarchical fixed sequence fail to reject the null hypothesis, then all untested endpoints will be evaluated as exploratory endpoints as hypothesis generating comparisons. All primary endpoints will be formally tested using the ITT population with multiple imputation as specified in Estimand 1. All secondary and exploratory endpoints will not be type I error controlled and will be hypothesis generating..

Primary Endpoint Efficacy Analysis

The dependent variable for the total corneal fluorescein staining and ocular discomfort will be based on intra-subject differences [REDACTED] For the primary analysis of the primary endpoints, subjects without a recorded value at Visit 7 (Day 29) will have missing values multiply imputed as specified in Estimand 1.

The change from baseline at Visit 7 (Day 29) of total corneal staining will be analyzed using an analysis of covariance (ANCOVA) model with terms for change in total corneal staining from baseline and treatment group. The change from baseline at Visit 7 (Day 29) of ocular discomfort will be analyzed using an ANCOVA model with terms for baseline discomfort score and treatment group.

The least squares mean of the intra-subject differences for each treatment group will be presented for the individual analyses with two-sided p-values and 95% confidence intervals.

As a sensitivity analysis, secondary examinations of the primary endpoints will also be presented. The sensitivity analyses of the primary endpoints will use multiple imputation and Last Observation Carried Forward (LOCF) imputation, followed by an ANCOVA. Analyses will also be executed using the PP population with observed/recorded data only.

Secondary Endpoint Efficacy Analyses

The method of analysis for secondary endpoints will be based on the distribution of the individual variable for analysis. Variables recorded on a continuous scale will be analyzed at each visit using two-sample t-tests and Wilcoxon rank sum tests. Each visit and treatment group will be summarized using descriptive statistics for the ITT population with observed data only. Changes from baseline will be summarized by visit and treatment using descriptive statistics and analyzed by visit using ANCOVA models with baseline value and treatment group, two sample t-tests and Wilcoxon rank sum tests on the ITT population with observed data only.

Safety Analyses

Adverse events will be coded using the Medical Dictionary for Regulatory Activities (MedDRA) dictionary. Frequencies and percentages will be provided per treatment group of subjects with treatment-emergent adverse events (TEAEs), serious TEAEs, and TEAEs causing premature discontinuation will be provided by treatment group. An adverse event is treatment emergent if it occurs or worsens after the first dose of randomized study treatment. Furthermore, frequencies will be given of subjects with TEAEs by system organ class and preferred term, by system organ class, preferred term and maximal severity, by system organ class, preferred term for treatment-related adverse events (AEs), by system organ class and preferred term for serious adverse events (SAEs); and by system organ class, preferred term, and day of onset. Separate analyses will be performed for ocular and non-ocular adverse events.

Other safety endpoints including visual acuity, slit-lamp biomicroscopy, intraocular pressure, and undilated fundoscopy will be summarized by treatment and visit using descriptive statistics. Change or shift from baseline will also be summarized where appropriate. For assessments performed by eye, both eyes will be summarized separately.

TABLE OF CONTENTS

Synopsis	3
Table of Contents	8
List of Abbreviations	12
1.0 Introduction	13
2.0 Study Objectives	14
3.0 Clinical Hypothesis	14
4.0 Overall Study Design	15
5.0 Study Population	16
5.1 Number of Subjects (approximate)	16
5.2 Study Population Characteristics	16
5.3 Inclusion Criteria	17
5.4 Exclusion Criteria	17
5.5 Withdrawal Criteria (if applicable)	19
6.0 Study Parameters	19
6.1 Efficacy Endpoints	19
6.1.1 Primary Efficacy Endpoints	19
6.1.2 Secondary Efficacy Endpoints	19
6.2 Safety Measures	20
7.0 Study materials	20
7.1 Study Treatments	20
7.1.1 Study Drug Formulation	20
7.1.2 Description of and Justification for the Route of Administration, Dosage, Dosage Regimen, and Treatment Period	20
7.1.3 Instructions for Use and Administration	21
7.2 Labeling, Packaging, Storage, Accountability, and Return or Disposal of Investigational Product	21
7.2.1 Labeling/Packaging	21
7.2.2 Storage of Investigational Product	21
7.2.3 Accountability of Investigational Product	21
7.2.4 Return or Disposal of Investigational Product	21
7.3 Other Study Supplies	21
8.0 Study Methods and Procedures	22

8.1	Subject Entry Procedures	22
8.1.1	Overview.....	22
8.1.2	Informed Consent.....	22
8.1.3	Washout Intervals	22

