3.0 CLINICAL HYPOTHESIS

The clinical hypotheses for this study is that low dose and high dose ST-100 Ophthalmic Solution twice daily (BID) is superior to its vehicle (BID) for the primary endpoints of signs and symptoms of dry eye, as follows:

- Sign: Pre-Controlled Adverse Environment (CAE®) total corneal fluorescein staining score on the Ora Calibra® scale, measured by [REDACTED]
[REDACTED]
- Symptom: Pre-CAE® ocular discomfort scale on the Ora Calibra® Ocular Discomfort scale, measured by [REDACTED]

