6.0 STUDY PARAMETERS

6.1 EFFICACY ENDPOINTS

6.1.1 Primary Efficacy Endpoints

The primary efficacy endpoint (sign) is:

- Total corneal fluorescein staining score on the Ora Calibra® scale, measured by [REDACTED]

The primary efficacy endpoint (symptom) is:

- Ocular discomfort score on the Ora Calibra® Ocular Discomfort Scale, measured by [REDACTED]

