## 1. Introduction

The purpose of this statistical analysis plan (SAP) is to describe the planned analyses and reporting for protocol amendment 1 dated 21-MAY-2021.

This SAP is being written with due consideration of the recommendations outlined in the most recent International Conference on Harmonisation (ICH) E9 Guideline entitled Guidance for Industry: Statistical Principles for Clinical Trials, the most recent ICH E9 (R1) Guideline entitled Guidance for Industry: Statistical Principles for Clinical Trials: Addendum: Estimands and Sensitivity Analysis in Clinical Trials, and the most recent ICH E3 Guideline entitled Guidance for Industry: Structure and Content of Clinical Study Reports.

This SAP describes the data that will be analyzed and the subject characteristics, efficacy, and safety assessments that will be evaluated. This SAP provides details of the specific statistical methods that will be used. The statistical analysis methods presented in this document will supersede the statistical analysis methods described in the clinical protocol. If additional analyses are required to supplement the planned analyses described in this SAP, they may be completed and will be identified in the clinical study report.

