## 3. Study Variables

### 3.1 Primary Endpoints

The primary efficacy endpoints are the following:

- Sign: Total corneal fluorescein staining score on the Ora Calibra® scale, measured by [REDACTED]  
[REDACTED]  
[REDACTED]
- Symptom: Ocular discomfort score on the Ora Calibra® Ocular Discomfort Scale, measured by [REDACTED]  
[REDACTED]

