## 18. Changes from Protocol-Stated Analyses

CFB-V2 Post as defined in section 9.3 of this SAP will be analyzed at Visit 3 (Day 2), Visit 4 (Day 4), Visit 5 (Day 8) Pre-CAE®, Visit 6 (Day 15) Pre-CAE®, and Visit 7 (Day 29) Pre-CAE®.

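### Does the synopsis success rule let high-dose ST-100 be called superior to placebo more widely than the staining test supports?

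*Protocol*

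**What the plan says.** The readable rule is in the protocol synopsis under Multiplicity Considerations. Four primary comparisons are tested in a fixed order: high-dose staining, high-dose discomfort, low-dose staining, low-dose discomfort. The first is described in full: change in total corneal fluorescein staining from Visit 2 pre-CAE to Visit 7 (Day 29) pre-CAE, high dose against placebo. If it is significant in favour of the high dose, "then the study will be considered a success and high-dose ST-100 will be declared to be superior to placebo".

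The numbered steps follow. Step 1 repeats the staining condition with its endpoint and opens the high-dose discomfort test. Step 2 begins "If the results of ocular discomfort score are statistically significant in favor of high-dose ST-100 over placebo" and opens low-dose staining. If any step fails, "then all untested endpoints will be evaluated as exploratory endpoints as hypothesis generating comparisons".

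Discomfort is a primary endpoint in its own right. Protocol 6.1.1 has a separate entry, "The primary efficacy endpoint (symptom) is", and SAP 3.1 lists "Symptom: Ocular discomfort score on the Ora Calibra® Ocular Discomfort Scale, measured by". Protocol 3.0 states the clinical hypothesis that each dose "is superior to its vehicle (BID) for the primary endpoints of signs and symptoms of dry eye, as follows", and then lists the sign and the symptom as two items.

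The synopsis section on the primary efficacy analysis presents least squares means, two-sided p-values and 95% confidence intervals for each primary analysis individually.

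Protocol 10.2 and 10.4.4 and SAP 3.4 and 9.5, where the hypotheses and multiplicity rules are set out in full, are largely or wholly redacted.

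**The concern.** Taken alone, the declaration is wider than its evidence. One test on a sign triggers both study success and a superiority statement with no endpoint in it. The symptom endpoint has equal primary status and has not yet been tested. If it then fails, the stated consequence covers only endpoints not yet tested. Discomfort would have been tested and lost, so that sentence does not reach it, and nothing expressly limits the declaration already made.

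The objective and the clinical hypothesis both speak of signs and symptoms. A reader who met an unqualified superiority statement could take it to mean that the whole hypothesis was met for the high dose, when half of it had failed.

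**Working it through.** **Which test the declaration refers to.** The declaring sentence is conditional on the results being significant in favour of the high dose. The only results described up to that point are those of the sentence before it, which gives endpoint, comparison, baseline and time point. Step 1 repeats the same trigger and names staining. Where the rule depends on discomfort, it says so (step 2). No other test could be the antecedent.

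**What is on record under each outcome.** Four ordered tests give five outcomes.

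| Tests won | Declaration made? | High-dose discomfort |
|---|---|---|
| 0 | No | Not formally tested; exploratory |
| 1 (high-dose staining) | Yes | Formally tested, null not rejected |
| 2 | Yes | Won |
| 3 | Yes | Won |
| 4 | Yes | Won |

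The declaration appears in four of the five rows, as with any rule that attaches success to the first step of a sequence. Only the row with one win matters here. In that row discomfort has its own estimate, confidence interval and p-value, and the formal sequence has stopped.

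**Type I error.** Inputs: 50 per arm (synopsis, Number of Subjects) and 10% dropout (synopsis, Sample Size), so 50 × 0.9 = 45 completers per arm. The type I error rate is redacted; two-sided 5% is assumed, in line with the 95% intervals. A simulation of the four-step sequence (400,000 runs, correlation 0.3 between endpoints) gave:

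- no effect on either endpoint: staining falsely won in 0.0248 of trials, in the favourable direction;
- staining effect 0.6 SD, no discomfort effect: staining won in 0.8117, discomfort falsely won in 0.024.

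Both false-win rates stay within 0.025. In the second scenario the declaration is made in about 81% of trials, and as a statement about staining it is true.

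**How often the split outcome occurs.** The plan's own power figures are not readable, so the effects here are assumed. Two-sample t-test, 45 per arm, two-sided 5%: power is 0.804, 0.467 and 0.290 for standardised effects of 0.6, 0.4 and 0.3. With a staining effect of 0.6, the share of staining wins followed by a discomfort loss is P(staining won, discomfort lost) / P(staining won):

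| Discomfort effect | Correlation 0 | Correlation 0.5 |
|---|---|---|
| 0.6 | 0.158 / 0.804 = 0.196 | 0.111 / 0.804 = 0.139 |
| 0.4 | 0.429 / 0.804 = 0.533 | 0.374 / 0.804 = 0.466 |
| 0.3 | 0.570 / 0.804 = 0.710 | 0.529 / 0.804 = 0.658 |

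At correlation 0 the share is simply one minus the power for discomfort: 1 − 0.804 = 0.196, 1 − 0.467 = 0.533, 1 − 0.290 = 0.710. The table therefore measures the chance of missing on discomfort. It would be identical if the clause named staining. The t-test is also only a stand-in for the planned ANCOVA on the ITT population with multiple imputation.

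**The case for a change.** The strongest case for a change is that a pre-specified conclusion should not need inference. The preceding sentence identifies the test, the next fixes the claim, and the claim drops the endpoint. Protocol 3.0 attaches superiority to named endpoints; the success rule does not. The remedy would be a few words with no effect on tests, error rate or sample size, and the assumed-effect figures show that a split result is not remote.

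Part of this stands: the clause would be tidier with the endpoint in it. The consequence does not follow. A claim conditional on one named test cannot properly be read as covering a second primary endpoint that has its own test and its own reported result.

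Going further, by reserving success or a signs-and-symptoms claim for a dose that wins both tests, would replace the sponsor's success criterion. Putting the sign first is a legitimate choice in a phase 2 trial, and Protocol 3.0 does not require a joint win.

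The SAP does not settle the matter either way. It says that "The statistical analysis methods presented in this document will supersede the statistical analysis methods described in the clinical protocol", and its multiplicity text is redacted, so the endpoint may already be named there. The silence of SAP 18 on the success rule is weak evidence that nothing was clarified. Naming an endpoint in a conclusion is not a changed analysis. SAP 18 also omits other differences: SAP 3.2 adds drop comfort at Visit 6 and removes Visit 4 from discomfort during CAE, compared with Protocol 6.1.2, and neither is listed.

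**Conclusion.** The observation is accurate for the isolated clause, but it calls for no change. Read with the sentence before it and with step 1, the declaration means superiority on change from baseline in total corneal fluorescein staining at Visit 7 pre-CAE, and an analyst writing the report would apply that scope. Adding the words would alter no test, estimate, p-value or decision.

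The 14% to 71% range rests on assumed effects (0.6 for staining; 0.3 to 0.6 for discomfort), correlations of 0 to 0.5, an assumed two-sided 5% level and 45 completers per arm. It describes power for discomfort and does not measure any harm from the wording. The conclusion rests on the readable synopsis and assumes that the redacted sections (Protocol 10.2 and 10.4.4, SAP 3.4 and 9.5) do not permit a symptom claim after a failed discomfort test. Nothing readable suggests that they do.
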